Study Title: A More Physiological Feeding Process in ICU:the Intermittent Infusion With Semi-solidification of nutrients

ClinicalTrails.gov ID: NCT 03017079

Date: 11/24/2016

Responsible party: [name]

Email: [contact]

Study Protocol

一. Purpose

- 1) To investigate whether intermittent feeding with semi-solid nutrients improves the enteral nutrition complications of diarrhea, reflux and aspiration;
- 2) Observe the feeding intolerance and the efficiency of the EN of critically ill patients;
- 3) Observe the blood sugar and insulin secretion;

二. Design and method

(1) Single center, randomized, single blind, controlled prospective study;

(2) Inclusion criteria:

- 1) not less than 14 years old of critical illnesses;
- 2) No long-term history of oral administration of gastrointestinal motility drugs;
- 3) Nasogastric tube for enteral nutritional support treatment;
- 4) No acute pulmonary infection;
- 5) No previous history of upper gastrointestinal surgery;

(3) exclusion criteria:

- 1) Refuse into the study;
- 2) Stay in ICU less than 3 days
- 3) acute pulmonary infection before entering the ICU;
- 4) have nutritional contraindications, such as intestinal ischemia or obstruction, gastrointestinal hemorrhage and so on;
- 5) No enteral nutrition received for less than 3 days;

(4) Abort criteria:

- 1) Abandoning treatment and discharge, resulting in incomplete data
- 2) EN contraindications nutrition during treatment;
- 3) Other condition of researchers think that patients are not fit to continue with the study;

(5) Groups

[figure not shown]
- 1) intermittent feeding (IF)
- 2) intermittent feeding with semi-solid nutrients (IS)

If you are assigned to the IS group, you should first receive a package of semi-solid agent to increase the intestinal nutrition viscosity. If you are assigned to the IF group, you will receive the routine nutrition treatment, and the treatment time for both groups is 3 days. After 3 days, you will receive routine enteral nutrition therapy. If there were serious enteral nutrition complications such as aspiration and abdominal distension within 3 days, the experiment would end. The treatment of the two groups only depends on whether semi-solid agent was added, while the rest of the treatment measures were consistent.

(6) Test

Blood (Microvascular blood sugar+ C-peptide release test), Secretions from the posterior pharynx and trachea;

三. Study process

四. How to protect high-risk groups or vulnerable groups

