The subject of this study is critically illnesses. Before entering the research group, the researchers must obtain the informed consent by the patient or the agent authorizer about the specific content of the study. For details, please refer to the informed consent.

五. Sample Size Calculating

According to the literature reported, the incidence of gastrointestinal intolerance (FI) is about 30.8%. We presume that $\delta = -0.05$, $\alpha = 0.025$, $\beta = 0.20$, the non-inferior efficiency test design is

$$(n_1 = n_2 = \frac{(Z_{1-\alpha/2} + Z_{1-\beta})^2 [\pi_1(1-\pi_1) + \pi_2(1-\pi_2)]}{(\pi_1 - \pi_2 - \delta)^2})$$

adopted and the formula is applied:

六. Data management and confidentiality

Data entry and management were designed in the form of a case report. A case report is a document designed according to the protocol for recording the data of each subject during the

trial.

All records relating to the subject's identity shall be kept confidential and shall not be made public to the extent permitted by applicable laws and/or regulations.

七. Informed consent

The subject of this study is critically illnesses. Before entering the research group, the researchers must obtain the informed consent by the patient or the agent authorizer about the specific content of the study. For details, please refer to the informed consent. The specific procedures for obtaining informed consent include oral and written informed consent from the physician to the patient, patient's family or authorized agent for the above study. The patient volunteered to participate in the study. Patients understand that they can withdraw from the study at any time for no reason, without affecting their future treatment. At the same time, the patient or the agent authorizer will obtain a copy of this informed consent. At the same time, the subjects included in this study were critically illnesses, and the subjects, told and signed, were mainly immediate family members.

八. Report of adverse events

After entering this study, there were some possible adverse reactions:

- (1) Diarrhea, which is most popular, may cause water and electrolyte disturbance in severe cases;
- (2) Nausea and vomiting, and stomach retention;
- (3) High and low blood sugar;
- (4) Aspiration is one of the more serious complications. Patients with weakness, old age or coma are more likely to have liquid diet reflux, especially those with esophageal reflux.
- (5) Take off and plug the pipe.

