Study Title: A More Physiological Feeding Process in ICU:the Intermittent Infusion With Semi-solidification of nutrients

ClinicalTrails.gov ID: NCT 03017079

Date: 11/24/2016

Responsible party: [name]

Email: [contact]

Statistical Analysis Plan

Data were expressed as means \pm standard deviations (SD) for quantitative variables and proportions for categorical and binary variables. Student's t test was used for statistical comparison between groups for continuous variables, general linear model for repeated measurement data, Fisher exact tests for categorical variables, and Mann-Whitney U test for ordinal variables. All tests for statistical significance were determined using an alpha level of 0.05. All analyses were performed using SPSS 17.0.

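### High and low blood sugar is a named risk, but no high or low glucose event is derived, so the only tests clearly assigned to the readings compare means

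*Protocol*

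**What the plan says.** Protocol section 八 (Report of adverse events), item 3, names "High and low blood sugar". The risk runs in both directions and has no cut-off, grade or event definition.

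Blood sugar also appears as an aim and as a measurement. Purpose 3 in section 一 reads "Observe the blood sugar and insulin secretion", and section 二 (6) lists "Blood (Microvascular blood sugar+ C-peptide release test), Secretions from the posterior pharynx and trachea". The readable text gives no sampling times and no number of readings per patient; any study-process figure could not be consulted.

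The SAP names neither blood sugar nor adverse events, so its handling of both has to be read from its general rules. Quantitative variables are given as means with "standard deviations (SD) for quantitative variables and proportions for categorical and binary variables". For testing, it states "Student's t test was used for statistical comparison between groups for continuous variables, general linear model for repeated measurement data". It also provides Fisher exact tests for categorical variables, all at an alpha of 0.05. It does not say which effect of the general linear model is to be tested.

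**The concern.** A two-directional risk is a statement about the tails of a distribution. The t test looks at the centre. If one feeding method produced more high and more low readings around a similar average, the mean difference could be close to zero while both named harms became more frequent.

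What is at stake is how a result of no difference in blood sugar would be read. It answers the metabolic question in purpose 3, but it could be taken as reassurance on item 3 of section 八, which it does not address. If cut-offs were instead chosen after the data were seen, any high or low result would be open to selection.

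**Working it through.** **Nothing to reproduce.** The documents state no glucose mean, SD, cut-off or event rate, and the sample size section concerns feeding intolerance. All numerical inputs below are therefore assumptions, used only to show direction: normal readings; low below 3.9 and high above 10 mmol/L; 30, 50 or 100 patients per arm.

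**Step 1: tail areas with equal means.** P(low) = Φ((3.9 − mean)/SD) and P(high) = 1 − Φ((10 − mean)/SD).

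| Mean | SD | Low | High |
|---|---|---|---|
| 8 | 2 | 2.0% | 15.9% |
| 8 | 3 | 8.6% | 25.2% |
| 8 | 3.5 | 12.1% | 28.4% |
| 8.5 | 2 | 1.1% | 22.7% |
| 8.5 | 2.5 | 3.3% | 27.4% |
| 8.5 | 3 | 6.3% | 30.9% |
| 8.5 | 3.5 | 9.4% | 33.4% |

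For example, at mean 8.5 and SD 3, (3.9 − 8.5)/3 = −1.53, which gives 6.3%. Relative to SD 2, low readings rise about 4-fold (8.6/2.0) to 6-fold (12.1/2.0) at mean 8, and about 3-fold (3.29/1.07) to 9-fold (9.44/1.07) at mean 8.5. The mean difference is zero throughout.

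**Step 2: what the tests detect.** Simulation with one value per patient, mean 8.5 in both arms, 2,000 runs, rejection at 0.05. The Fisher test here is on any value outside 3.9 to 10.

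| SDs | n per arm | t test | Fisher | Levene |
|---|---|---|---|---|
| 2 vs 3 | 30 | 4.4% | 14% | 48% |
| 2 vs 3 | 50 | 4.9% | 22% | 72% |
| 2 vs 3 | 100 | 5.7% | 48% | 96% |
| 2 vs 3.5 | 30 | 4.5% | 26% | 75% |
| 2 vs 3.5 | 50 | 4.7% | 43% | 94% |
| 2 vs 3.5 | 100 | 5.4% | 77% | 100% |

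The t test stays at its error rate. A test of spread is the most sensitive here, but it does not say whether readings went low or high, and those are the named harms.

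**Step 3: the repeated-measures model.** Assumptions: 50 per arm, four readings, between- and within-patient SD 1.4 each.

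- Swings of ±0.5 mmol/L at the same times in every patient: group effect 5%, group-by-time 86%. At ±1.0, group-by-time reaches 100%.
- Swings of ±2.0 at times that differ between patients (1,000 runs): group effect 4.9%, group-by-time 5.6%.

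The model is therefore blind only in part.

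**Step 4: limits of an event comparison.** With 50 per arm, one reading each, and low rates of 1.07% and 6.26%, the expected counts are 0.5 and 3.1. For 0 against k events, the two-sided Fisher p is 2·C(50,k)/C(100,k): 0.24 for k = 3, 0.056 for k = 5 and 0.027 for k = 6. Lows alone would rarely reach significance.

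A per-patient rate also depends on the number of readings. With four independent readings, 1 − (1 − 0.0107)⁴ = 4.2% and 1 − (1 − 0.0626)⁴ = 22.8%. The number of readings therefore has to be reported beside the rate.

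**The case against.** A reader might infer that the plan summarises blood sugar only as a mean, and so cannot show the risk at all. The documents do not support that reading, for four reasons.

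- The SAP prints the SD beside the mean. A wider spread would be visible, though untested and without direction.
- "general linear model for repeated measurement data" can include a group-by-time effect, which Step 3 shows can find opposite shifts at common times.
- The SAP never says that the adverse event will be analysed as a mean. An adverse-event entry is naturally yes or no, and proportions and Fisher tests are already in the SAP.
- No text says that the blood sugar test was included for this risk. It fits purpose 3, for which comparing means is ordinary.

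A fair critic would add that nothing in the documents suggests the semi-solid agent widens glucose swings around an unchanged mean. The fold increases come entirely from assumed inputs, and the event comparison has low power in small arms.

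All of this stands, and it limits the point. It does not remove it. The Fisher test has no defined glucose event to act on, the SAP does not name group-by-time as the effect of interest, and swings at patient-specific times escape both effects.

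**Conclusion.** The concern holds as a gap between a named two-directional risk and the analysis clearly assigned to the readings. No high or low event is derived, and the tests that apply without adding an undefined variable compare means. A change in spread, or swings at times that differ between patients, would go untested.

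That a mean comparison misses a pure change in spread does not depend on the assumed figures. How large the missed harm could be depends on them entirely, and the documents neither support nor exclude a particular size. This is a secondary safety matter and does not touch the outcome used for the sample size. It is worth correcting because the correction is cheap, not because the plan is shown to hide a harm.

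**What to change.** Add to the SAP:

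1. From the blood sugar readings already taken, derive for each patient two separate yes/no variables over the 3-day treatment period: at least one low reading, and at least one high reading. The investigators set the cut-offs and fix them before analysis.
2. Report each as a proportion per arm with the difference and its confidence interval, and compare it with the Fisher exact test already in the SAP.
3. State the number of readings and days observed per arm. Protocol section 二 (5) ends the experiment early after certain serious complications, which shortens the time in which an event can be recorded.
4. Keep the mean comparison for purpose 3, and draw no glucose-safety conclusion from it alone.

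The cost is a few lines of SAP text and two derived variables, with no new samples. The downside is two further secondary comparisons with limited power, especially for low readings. They should be presented as safety estimates, and a non-significant result should not be read as evidence of no harm.

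### Tube displacement and blockage are listed as a risk of a trial that thickens tube feed in one arm only, but they are in no stated purpose and no between-arm comparison is planned

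*Protocol*

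**What the plan says.** **Route and contrast.** The third inclusion criterion in Protocol section 二 (2) is "Nasogastric tube for enteral nutritional support treatment", so every patient is tube-fed. Under section 二 (5), Groups, a patient allocated to the semi-solid arm (IS) is told "you should first receive a package of semi-solid agent to increase the intestinal nutrition viscosity". The same section limits the contrast to that agent: "The treatment of the two groups only depends on whether semi-solid agent was added". Treatment lasts 3 days in both arms.

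**Listed risks.** Section 八 opens with "After entering this study, there were some possible adverse reactions" and gives five items for the study as a whole, not for one arm. The fifth is "Take off and plug the pipe".

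**Stated purposes (section 一).** The first asks whether semi-solid feeding "improves the enteral nutrition complications of diarrhea, reflux and aspiration". The second is "Observe the feeding intolerance and the efficiency of the EN of critically ill patients". The third covers blood sugar and insulin secretion.

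**SAP.** Its single paragraph assigns tests to types of variable, with Fisher's exact test for categorical data. It names no endpoint, no safety analysis and no measure of feed delivered.

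**The concern.** The randomised difference is a thicker feed passing through a narrow tube. Whether the tube stays patent and in place is an obvious mechanical question about such a feed, and the protocol lists it as a risk. Yet the trial sets out to compare gastrointestinal, aspiration and metabolic results and leaves this risk out.

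What is at stake is the balance of the conclusion. A report that semi-solid feeding reduces complications would be incomplete if blocked or dislodged tubes had become more common and nobody had counted them by arm. The Protocol's closing sentence also says that participation brings patients no extra risk. Without counts by arm, the trial cannot check that statement for tube events. If the events are not recorded at the time, an analyst may be unable to recover them later.

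**Working it through.** There is no stated figure to reproduce, because neither document gives a tube-event rate. The check is a comparison of texts, followed by a short illustration of why no size can be given.

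**Step 1. Match each listed reaction (section 八) to a purpose (section 一).**

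| Item in section 八 | Matching purpose |
|---|---|
| (1) Diarrhea | 1 |
| (2) Nausea, vomiting, gastric retention | 2, read as part of feeding intolerance, which the protocol does not define |
| (3) High or low blood sugar | 3 |
| (4) Aspiration | 1 |
| (5) Tube displacement and blockage | none |

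Four of five items match. The exception is item (5).

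**Step 2. Look for a comparison elsewhere.** The SAP would supply a suitable test if a yes/no tube variable existed, but nothing in either document creates that variable, defines it or says it will be compared. Because the SAP names no endpoint at all, its silence is not specific to tube events. The specific evidence is the mismatch in Step 1.

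**Step 3. Ask whether delivered feed is covered.** Purpose 2 includes EN efficiency. It could mean delivered versus prescribed feed, but neither document defines it or ties it to the diarrhea and reflux results. Even under that definition it would show a shortfall in delivery without showing that a tube event caused it.

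**Step 4. Size.** Suppose a share *e* more patients in the semi-solid arm than in the control arm (IF) have an interruption from a tube event, and their risk of diarrhea or reflux falls by a fraction *r*. With a control rate *p* and no other effect of the agent, the apparent reduction is *p × e × r*. Take *p* = 0.308, the Protocol's feeding-intolerance rate, only as a stand-in. Both *e* and *r* are assumptions.

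- *e* = 0.05, *r* = 0.5: 0.308 × 0.05 × 0.5 = 0.0077, or 0.8 points
- *e* = 0.10, *r* = 0.5: 0.308 × 0.10 × 0.5 = 0.0154, or 1.5 points
- *e* = 0.10, *r* = 1: 0.308 × 0.10 × 1 = 0.0308, or 3.1 points
- *e* = 0.20, *r* = 1: 0.308 × 0.20 × 1 = 0.0616, or 6.2 points

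If 20% of IS patients and 10% of IF patients had an interruption, *e* would be 0.10, and the last figure would halve to 3.1 points. The result depends entirely on the assumed inputs, so it is no estimate for this trial.

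**The case against.** **Tube events are not ignored.** They appear under a heading on adverse-event reporting, section 六 provides for a case report form, and a yes/no event would fall under the SAP's Fisher test. The documents define no outcome in detail, so the lack of definition is general. This is fair, and it limits the point to the absence of a named outcome, a recording rule and a stated comparison. It does not explain why only this item has no matching purpose.

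**Material is missing from the text available.** The figure under Groups is not shown, section 三 has a heading but no text, and the case report form is not included. Recording details could be there, so it cannot be said that tube events go unrecorded. The purposes, the adverse-event list and the SAP are legible, however, and none makes tube events an outcome.

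**A stronger reading is tempting: that blocked tubes would make semi-solid feed look better on diarrhea and reflux because less is delivered, unseen, perhaps by more than the 5-point margin.** The documents do not support it, for these reasons:

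- No passage says that the thickened feed blocks or dislodges tubes.
- Only an excess of events in the semi-solid arm matters, and control patients are tube-fed too.
- A fall in diarrhea that comes through reduced delivery is still part of the randomised effect of the feed. The issue is how to interpret it.
- EN efficiency may already show under-delivery.
- The margin is given with a feeding-intolerance rate. Setting an assumed diarrhea or reflux shift against it mixes outcomes.

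The list of specimens in section 二 (6) and the stopping examples in section 二 (5) are not evidence either. Diarrhea is not on the first list, and the second is explicitly only examples.

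**Conclusion.** The concern holds as a gap in the safety comparison. Tube displacement and blockage is the only one of five listed reactions with no corresponding purpose, and it is the mechanical harm that a more viscous feed might plausibly raise. No between-arm comparison of it is planned.

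The size is unknown, and the illustrative figures should not be quoted as an expected bias. The conclusion rests on two readings: that item (5) means displacement and blockage of the feeding tube, and that nausea, vomiting and retention belong to feeding intolerance. It also assumes that the missing figure and section 三 do not already name tube events as an outcome. This is a worthwhile, inexpensive safety improvement. It does not show that the trial's main comparison is invalid.

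**What to change.** 1. Name tube blockage and tube displacement as safety outcomes. Record each separately, yes or no per patient, in both arms, within the 3 treatment days.
2. Compare each by arm with the Fisher exact test already in the SAP, and report the counts. The trial is not sized for this comparison, so a non-significant result should not be read as showing no difference.
3. Define EN efficiency as delivered versus prescribed feed, and record both quantities.
4. Report tube events and delivered feed beside the results for diarrhea, reflux and aspiration.

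The cost is a few more case report form items (two yes/no fields plus the feed quantities), two more comparisons, and a safety result that may be unfavourable to the semi-solid arm. None of this changes treatment or clinical management.

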Patients will not receive additional treatment or take additional risks for participating in the study

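### The Protocol denies any additional treatment or risk from taking part, but the IS arm is defined by an added agent and adverse reactions are listed as possible after study entry

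*Protocol*

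**What the plan says.** Four places in the Protocol bear on this point.

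- **Closing sentence, after the list in section 八 (Report of adverse events):** "Patients will not receive additional treatment or take additional risks for participating in the study". It carries no qualifier.
- **Section 二 (5), Groups:** for the experimental arm, "If you are assigned to the IS group, you should first receive a package of semi-solid agent to increase the intestinal nutrition viscosity". For the comparator, "If you are assigned to the IF group, you will receive the routine nutrition treatment". The section then sums up the contrast: "The treatment of the two groups only depends on whether semi-solid agent was added, while the rest of the treatment measures were consistent".
- **Section 二 (6), Test:** "Blood (Microvascular blood sugar+ C-peptide release test), Secretions from the posterior pharynx and trachea". The tests are not restricted to one arm, and the section does not say which of them would be done anyway in usual care.
- **Section 八, opening line:** "After entering this study, there were some possible adverse reactions". Five items follow: diarrhea; nausea, vomiting and gastric retention; high and low blood sugar; aspiration; and, last, "Take off and plug the pipe".

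Sections 四 and 七 rest the protection of these critically ill patients on informed consent, mostly given by close relatives, and refer to the consent form for the details.

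**The concern.** The closing sentence is a participant-protection statement, and it makes two claims: nothing is added to treatment, and nothing is added to risk. The rest of the Protocol describes a randomised trial whose only treatment contrast is something added. A reader who relies on the closing sentence, such as an ethics committee or someone drafting patient information from the Protocol, would get a wrong account of what the IS arm receives and an assurance about risk that the trial has not earned.

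The statement matters more here than in many trials. The patients are critically ill, can be as young as 14, and mostly have consent given for them by family.

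**Working it through.** The documents give no figure for this point and none is needed. The check sets the passages side by side, one clause at a time.

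**Treatment clause**

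1. The Groups section gives the IF arm routine nutrition and returns both arms to routine enteral nutrition after 3 days. Routine care is therefore the reference.
2. The same section gives the IS arm an agent that the IF arm does not receive, and says that this agent is the only treatment difference.
3. An IS patient thus receives something outside the routine reference, and receives it because of allocation in the study. That is additional treatment from participation.
4. The clause is therefore untrue for every IS patient. The formula in section 五 sets n1 = n2, so the share of patients is n1 / (n1 + n2) = 1/2. As far as treatment goes, the documents do not contradict the clause for IF patients.

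**Risk clause**

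1. Section 八 introduces its five items as reactions possible after study entry, and the denial of added risk follows directly.
2. The Groups section provides for ending a patient's experiment if serious feeding complications occur within the 3 days, with aspiration and abdominal distension as examples.
3. Section 一 (Purpose) asks whether IS improves diarrhea, reflux and aspiration. While that question is open, the Protocol has no basis for saying that IS adds no risk.
4. None of this shows that the agent does add risk. The listed reactions are general complications of tube feeding and could occur in either arm. The documents give no rate by arm and no direction. The risk clause is unsupported, which is a weaker finding than false.

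**Tests**

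The C-peptide release test matches the third purpose (blood sugar and insulin secretion), and the secretion samples plausibly serve the first (reflux and aspiration). Capillary glucose may well be usual care. Any sample taken only for the study would be a further departure from the closing sentence, in either arm. The Protocol does not say which samples those are, so the finding does not rest on them.

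**Coverage of the listed harms**

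| Item in section 八 | Covered by a stated purpose? |
|---|---|
| Diarrhea | Yes, purpose 1 |
| Nausea, vomiting, gastric retention | Yes, read as feeding intolerance, purpose 2 |
| High and low blood sugar | Yes, purpose 3 |
| Aspiration | Yes, purpose 1 |
| Tube dislodgement or plugging | No |

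Four of the five items overlap the stated purposes; only tube events fall outside them.

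**The case against.** The strongest defence is that this is one badly worded sentence with no effect on the statistics. Correcting it changes no sample size, endpoint or planned test. The sentence may have been meant to say that nothing happens beyond what the Protocol describes, and the Groups text, written in the second person as if for patients, openly discloses the agent. That defence limits the consequences but does not rescue the sentence, which has no such qualifier and contradicts the Groups section as it stands.

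Four stronger readings are tempting, and the objection to each stands.

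- **That families were misled.** The consent form is not among the documents, and the Protocol defers to it. What relatives were told cannot be judged from here.
- **That thickened feed plugs more tubes.** A reader might infer this from raised viscosity and the inclusion criterion on nasogastric feeding. No sentence gives the agent's route, none links it to plugging, and no rate is given.
- **That the denial removed the reason to compare harms.** The coverage table shows otherwise: most listed harms fall under the study's own purposes.
- **That tube events are ignored.** They are listed under adverse-event reporting. The SAP assigns Fisher's exact test to categorical variables and names no individual outcome at all, so the absence of a named tube comparison is not peculiar to tube events. The complications that end the experiment are given as examples, so plugging's absence there proves little.

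**Conclusion.** The contradiction is real and should be corrected. The treatment clause is untrue for all IS patients, half of those randomised under equal allocation. That conclusion needs only the Protocol's own contrast between the added agent and routine nutrition. The risk clause is a blanket denial without support, set directly after a list of possible reactions; the documents do not establish that the agent increases any particular harm.

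The finding concerns the Protocol's own statement. It does not extend to the content of consent actually given, to a mechanical hazard of the agent, or to the validity of the planned comparisons. Whether the listed tests add burden in both arms depends on which of them exceed usual care, and the Protocol leaves that unstated.

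**What to change.** **Correction.** Reconcile the closing sentence with the Groups, Test and adverse-event sections by replacing it with a statement that:

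- IS patients receive an added agent that thickens the feed, which IF patients do not receive;
- the listed blood and secretion samples are taken, identifying any that go beyond usual care;
- the reactions listed in section 八, including tube dislodgement or plugging, are possible risks.

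Then check that the consent form says the same, and amend it if it does not.

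**Suggestion, not the correction of an error.** Report the number of patients in each arm with tube dislodgement or plugging beside the feeding-intolerance result, compared with the Fisher test that the SAP already specifies. The event is already listed for reporting. The documents give no expected rate, so the power of that comparison is unknown, and a non-significant result should not be presented as evidence of no difference.

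**Cost.** A wording amendment to the Protocol, and to the consent form if needed; a less favourable risk statement; and, if the suggestion is taken, one more comparison. Sample size and existing analyses are unchanged.
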